3.1.1 Hypotheses

H_o : The five (5) year chronic lead-related complication-free rate \leq 92.5%

H_a : The five (5) year chronic lead-related complication-free rate $>$ 92.5%

The null hypothesis will be rejected if the lower one-sided 95% confidence bound for the chronic lead-related complication-free rate is greater than 92.5%.

3.1.2 Sample Size

Based on the calculations below, the sample size for this registry is approximately 1700 patients implanted with the ACUITY Spiral Lead with a successful LATITUDE data transmission. An exact binomial calculation with the parameters in Table 3-1: **Sample Size Parameters and Justification** was used to determine the approximate sample size necessary to detect a clinically meaningful change with 80% power and a one-sided α -level of 0.05. An annual attrition rate of 10% is assumed over the five-year follow-up.

Table 3-1: Sample Size Parameters and Justification

Primary Endpoint	N	P	Δ	95% Confidence Boundary	Justification
Chronic LV lead-related complications	1000	94.5%	2.0	92.5%	Prospectively defined based on predicate data from EASYTRAK lead*. 95% confidence boundary is clinically acceptable.

*The EASYTRAK lead was studied as part of the CONTAK CD/EASYTRAK Post Approval Study (PMA P010012). Mean implant duration was 26±13 months, with a cumulative implant duration of over 25,000 patient months. The 3 year chronic lead-related complication free rate was 97.9% using Kaplan-Meier methods. Assuming a continued 1.7% annual rate (consistent with observed year to year changes in rates from previous pre-market LV lead studies) from years 3 to 5 would result in an estimated 94.5% chronic complication free-rate at 5 years for the EASYTRAK LV lead.

3.1.3 Statistical Methods

3.1.3.1 Overview

When the final study subject reaches five (5) years of follow-up, the primary analysis will be performed based on the Kaplan-Meier method for the estimation of the five (5) year chronic lead-related complication-free rate, including the lower one-sided 95% confidence interval. The censoring mechanism of the Kaplan-Meier analysis incorporates all available data on study subjects, including those that withdrew or were lost-to-follow-up.

3.1.3.2 Subjects included in Endpoint Analysis

The Kaplan-Meier analysis will begin at 45 days post-implant for each patient. All patients that are successfully implanted with the ACUITY Spiral Lead and still actively followed in the study at 45 days post implant will be included in the analysis.

3.1.3.3 Adverse Events Included in Endpoint

The determination for inclusion of adverse events in the endpoint analysis will be made by an independent Clinical Events Committee (CEC). The adverse event will count against the endpoint if a consensus of CEC members agrees the event meets the definition

of inclusion into the endpoint. Refer to the CEC Charter (CDM00060021) for more information.

LV lead-related adverse events within 45 days following invasive cardiac surgery (device implant, PG change-out, cardiac catheterization, etc.) need to be reported, but will be omitted from the endpoint analysis. In addition, the following events will be collected, but will be excluded from the endpoint analysis unless determined by the Clinical Events Committee (See Protocol Section 4.2.2) to be attributed to a structural lead failure:

- Inability to place the LV lead
- Implant procedure related complications such as CS dissection, CS perforation, pneumothorax, arrhythmias, cardiac tamponade, hematoma
- LV Lead-related thrombosis
- In-patient damage to LV lead (e.g., accidental cut to lead body during pocket revision, device replacement, etc.)
- LV Lead dislodgments up to 180 days post implant procedure
- Twiddler's syndrome leading to LV lead dislodgment
- High LV pacing threshold, intermittent LV capture, no capture of LV lead
- Diaphragmatic/pectoral stimulation
- Infection
- Atrial lead, ICD lead, or generator adverse events requiring additional interventions
- Non-LV lead-related hospitalizations
- Non-LV lead-related death
- Lead revisions to optimize therapy
- Exit block
- Physiologic oversensing or undersensing

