4. ENDPOINTS AND DATA ANALYSIS

4.1. Endpoints

4.1.1. Primary Endpoint: Chronic LV Lead-Related Complication-Free Rate

4.1.1.1. Description and Rationale for Endpoint Selection

The ACUITY Spiral Lead will be evaluated by a chronic LV lead-related complication-free rate over a five year follow-up period.

The primary endpoint analysis will include confirmed chronic LV lead related complications that result in permanent loss of therapy, invasive intervention, injury or death.

LV lead-related adverse events within 45 days* following invasive cardiac surgery (device implant, PG change-out, cardiac catheterization, etc.) need to be reported, but will be omitted from the endpoint analysis. In addition, the following events will be collected, but will be excluded from the endpoint analysis unless determined by the Clinical Events Committee (See Section 4.2.2) to be attributed to a structural lead failure.

- Inability to place the LV lead
- Implant procedure related complications such as CS dissection, CS perforation, pneumothorax, arrhythmias, cardiac tamponade, hematoma
- LV Lead-related thrombosis
- In-patient damage to LV lead (e.g., accidental cut to lead body during pocket revision, device replacement, etc.)
- LV Lead dislodgments up to 180 days post implant procedure
- Twiddler's syndrome leading to LV lead dislodgment
- High LV pacing threshold, intermittent LV capture, no capture of LV lead
- Diaphragmatic/pectoral stimulation
- Infection
- Atrial lead, ICD lead, or generator adverse events requiring additional interventions
- Non-LV lead-related hospitalizations
- Non-LV lead-related death
- Lead revisions to optimize therapy
- Exit block
- Physiologic oversensing or undersensing

* Based on review of previous clinical studies, using a maximum of 45 days post implant gives centers an opportunity to enroll patients while allowing for a consistent time period for enrollment post implant and assessing acute adverse events without excluding adverse events that characterize long-term lead performance.

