4.2. Data Analysis

4.2.1. Endpoint Analysis

For the ACUITY Spiral Lead, the primary endpoint for this registry will evaluate the proportion of patients without a chronic ACUITY Spiral Lead-related complication within five years post-implant. When the final patient reaches five years of follow-up, the primary analysis will be based on the Kaplan-Meier method for the estimation of the five-year chronic lead-related complication-free rate, including the lower one-sided 95% confidence interval. The censoring mechanism of the Kaplan-Meier analysis incorporates all available data on patients, including those that withdraw or are lost to follow-up.

The Kaplan-Meier analysis will begin at 45 days post-implant for each patient. All patients that are successfully implanted with the ACUITY Spiral Lead and still actively followed in the study at 45 days post implant will be included in the analysis. The endpoint adverse events are defined as confirmed lead-related complications meeting the criteria in section 4.1.1.1. The

[†] The EASYTRAK lead was studied as part of the CONTAK CD/EASYTRAK Post Approval Study (PMA P010012). Mean implant duration was 26±13 months, with a cumulative implant duration of over 25,000 patient-months. The 3 year chronic lead-related complication free rate was 97.9% using Kaplan-Meier methods. Assuming a continued 1.7% annual rate (consistent with observed year to year changes in rates from previous pre-market LV lead studies) from years 3 to 5 would result in an estimated 94.5% chronic complication free-rate at 5 years for the EASYTRAK LV lead.

determination for inclusion of adverse events in the endpoint analysis will be made by an independent Clinical Events Committee. Additionally, since this registry is focused on chronic LV-lead performance, acute adverse events associated with attempted leads will not be included in this analysis as they would fall within the 45 days of an invasive cardiac surgery, therefore not meeting the criteria outlined in Section 4.1.1.1.

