3 ENDPOINT ANALYSIS

3.1 Primary Endpoint

The ACUITY Spiral Lead will be evaluated by the chronic LV lead-related complication-free rate over a five year follow-up period. The primary endpoint analysis will include confirmed chronic LV lead related complications that result in permanent loss of therapy, invasive intervention, injury or death, and are deemed attributable to a structural lead failure by an independent Clinical Events Committee (CEC).

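### Minor: the 45-day omission also runs after later procedures and, as worded, has no structural-failure exception, so a late confirmed lead failure could go uncounted

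*SAP*

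**What the plan says.** SAP 3.1.3.3 and Protocol 4.1.1.1 state two exclusions in consecutive sentences, in essentially the same words.

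- **Time window.** For the endpoint analysis, LV lead-related events occurring "within 45 days following invasive cardiac surgery (device implant, PG change-out, cardiac catheterization, etc.) need to be reported, but will be omitted". The triggers include generator change-out and cardiac catheterization as well as implant. This sentence has no exception.
- **Event list.** A further set of events, introduced as additional to the first, is "excluded from the endpoint analysis unless determined by the Clinical Events Committee (See Protocol Section 4.2.2) to be attributed to a structural lead failure". One listed item is "In-patient damage to LV lead (e.g., accidental cut to lead body during pocket revision, device replacement, etc".

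The protocol's footnote on the 45 days says that "using a maximum of 45 days post implant gives centers an opportunity to enroll patients" and gives as an aim "assessing acute adverse events without excluding adverse events that characterize long-term lead performance". It speaks only of time since implant.

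SAP 3.1 counts confirmed chronic complications with serious consequences that are "deemed attributable to a structural lead failure by an independent Clinical Events Committee". It mentions no 45-day window. SAP 3.1.3.3 leaves inclusion to CEC consensus on whether the event meets the definition, and adds: "Refer to the CEC Charter (CDM00060021) for more information".

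**The concern.** The registry exists to find time-dependent failure modes of the lead (Protocol 1.1). A conductor or insulation failure three or four years after implant is the kind of event it should count. If that failure is dated within 45 days after a generator change-out or a catheterization, the window sentence omits it, and the CEC exception does not reach that sentence by its grammar.

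CEC discretion does not clearly rescue such an event, because the committee judges it against a definition that includes the omission. If the lead then goes out of service, Protocol 6.3 withdraws the patient. With no endpoint event recorded, SAP 4.1 censors the patient, so the failure enters the curve as a censored observation.

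Two careful readers could therefore produce different event counts for the only primary test. The literal reading errs in one direction, towards a higher complication-free rate.

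**Working it through.** **1. The passages side by side**

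- The exception clause belongs to the list sentence only. Protocol 4.2.1 uses the window as sufficient in itself: acute events with attempted leads are left out "as they would fall within the 45 days of an invasive cardiac surgery, therefore not meeting the criteria outlined in Section 4.1.1.1". That passage does not concern late failures, but it shows the window applied without reference to the exception.
- The footnote gives no reason for extending the window to later procedures, and its aim is to keep events that describe long-term performance.
- Damage to the lead during device replacement is on the list and so carries the exception. If it is found within 45 days of the replacement, the window sentence omits it without exception. The two sentences can then give opposite answers for one event.
- Protocol 6.3.1 requires inspection of the proximal lead and header at change-outs. Neither document says whether a defect found during the change-out counts as following it.

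**2. The plan's own figures**

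Inputs (Protocol 4.1.1.3, SAP 3.1.2): N = 1000, 94.5% against 92.5%, one-sided 0.05, 80% power, 10% annual attrition.

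- Exact binomial, n = 1000: success needs at least 939 complication-free patients (at most 61 failures). Alpha is 0.0493 and power 0.8175.
- Attrition: 1000/0.9^5 = 1694, stated as 1700; 1700 × 0.9^5 = 1004.

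The stated figures reproduce and are not in dispute.

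**3. Share of failures affected**

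Let q be the share of otherwise countable failures dated within 45 days after a later procedure. The documents give neither q nor the frequency of such procedures, so both are assumptions. With failures spread evenly from day 45 to day 1826:

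q = (later procedures per patient) × 45/(1826 − 45)

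Apparent rate at a true 92.5% = 1 − 0.075 × (1 − q)

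**4. Effect on the test**

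Simulated Kaplan-Meier analysis with the linear Greenwood bound of SAP 3.1.3.4: 1700 implanted, 10% annual attrition, patients lost before day 45 excluded, constant hazard from day 45, omitted patients kept at risk. There were 100,000 data sets at a true 92.5% (Monte Carlo SE at most 0.0009) and 50,000 at 94.5% (SE at most 0.0013).

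| Later procedures per patient | q | Apparent rate, true 92.5% | Events omitted, of about 99 | P(success), true 92.5% | Events omitted, of about 72, true 94.5% | Power, true 94.5% |
|---|---|---|---|---|---|---|
| 0 | 0 | 92.50% | 0 | 6.1% | 0 | 91.2% |
| 0.25 | 0.63% | 92.55% | 0.6 | 6.9% | 0.5 | 92.0% |
| 0.5 | 1.26% | 92.59% | 1.3 | 7.7% | 0.9 | 92.8% |
| 1 | 2.53% | 92.69% | 2.5 | 9.7% | 1.8 | 94.2% |

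The 6.1% in the first row does not come from the omission rule. Only the rise above it does.

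A cross-check with the exact binomial rule of step 2 shows the same pattern: 4.9% with no omission, 5.9% at 1% omitted and 7.6% at 2.5% omitted.

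**The case against.** The best case for the plan is that this is a deliberate endpoint rule. Both documents carry it and both name the later procedures, and leaving out events close to an invasive procedure is a legitimate design choice. The footnote explains the length of the window, and its silence on later procedures is not a contradiction. The list items keep a purpose without overriding the window, since damage at a replacement may show only after day 45. A failure that prompts a revision precedes that surgery and so is not in its window. Adjudications are shown to FDA every six months (SAP 5.2), and the CEC charter may already deal with the point.

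Most of this stands, and it limits the point to a minor one. A reader might infer that the plan contradicts its own endpoint definition. The documents do not support that: SAP 3.1 leaves chronic undefined, and structural attribution is only one of its conditions. A reader might also infer that the rule seriously inflates false success. That would need a large q, for which the documents give no basis.

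What does not fall is the wording. Reporting adjudications to FDA does not change the rule. The modified curve in SAP 5.3 is a separate analysis and does not say whether the later-procedure window carries over. The charter cannot be checked from these documents.

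**Conclusion.** The point holds as a minor one. As written, a CEC-confirmed structural failure within 45 days after a late procedure is not counted, and neither document gives a reason for that. The effect runs only towards rejecting H0.

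It is probably small: about 0.6 to 2.5 of 99 events, and a chance of success at a true 92.5% of about 7% to 10% instead of about 6%. At the planned 94.5%, fewer than 2 of 72 events are affected. These figures rest on an assumed 0.25 to 1 later procedure per patient and on failures spread evenly in time. Fewer procedures would make the effect smaller. If procedures tend to cause or reveal failures, it would be larger. The point falls away if the charter already extends the exception, apart from copying that wording into the SAP and protocol.

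**What to change.** In SAP 3.1.3.3 and Protocol 4.1.1.1:

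1. Leave the window after the initial implant as it is. SAP 3.1.3.2 starts the Kaplan-Meier analysis at day 45 in any case. (SAP 3.1.3.4 gives implant as the start. That discrepancy is separate, and this change does not depend on it.)
2. For windows after later procedures, attach the exception that the list already carries: events are omitted unless the CEC attributes them to a structural lead failure. No new test of whether the procedure caused the failure is needed, because SAP 3.1 already requires structural attribution for every counted event.
3. State that a defect found during a change-out is not omitted merely because of that change-out.
4. Align the wording with the CEC charter.

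Document this under SAP 5.5 before the 5-year analysis, apply it to events already omitted, and report the 5-year rate under both the existing and the extended rule. If the sponsor prefers not to amend the primary rule, prespecify the extended rule as a supportive analysis.

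**Cost.** A short documented amendment, with IRB approval of the protocol change (Protocol 8), and re-review of a few events. The CEC already receives all PG- or lead-related events (Protocol 4.2.2). The registry is past its 30-month report and its curves are seen every six months, which is why both results should be shown. The change can only add events, so it cannot raise the chance of false success. The estimated rate may be slightly less favourable. Simulated power at 94.5% with all such events counted is about 91%, above the planned 80%.

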3.1.3.4 Tests to be performed

The primary endpoint will evaluate the 5-year chronic lead-related complication-free rate, calculated using Kaplan-Meier (product-limit) methods. The Kaplan-Meier analysis will begin at the time of implant for each study subject. The null hypothesis will be rejected in favor of the alternative if the lower one-sided 95% confidence limit for the chronic lead-related complication-free rate is greater than 92.5%. This analysis will be performed after the last subject has completed 5 years of follow-up. The 5-year survival estimate will be calculated using product-limit survival estimates as follows:

Let $t_1 < t_2 < \dots < t_D$ represent the distinct event times. For each $i = 1, \dots, D$, let n_i be the number of surviving units (the size of the risk set) just prior to t_i . Let d_i be the number of units that fail at t_i , and let $s_i = n_i - d_i$.

The Kaplan-Meier (product-limit) estimate of the survivor function at t_i is the

$$\text{cumulative product } \hat{S}(t_i) = \prod_{j=1}^i \left(1 - \frac{d_j}{n_j}\right)$$

All the estimators are defined to be right continuous. The corresponding estimate of the standard error is computed using Greenwood's formula (Kalbfleisch and Prentice; 1980) as

$$\hat{\sigma}(\hat{S}(t_i)) = \hat{S}(t_i) \sqrt{\sum_{j=1}^i \frac{d_j}{n_j s_j}}$$

The lower 95% confidence bound at t_i is calculated in SAS as follows:

$$100 * (\hat{S}(t_i) - \text{probit}(0.95) * \hat{\sigma}(\hat{S}(t_i)))$$

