3.1.3.5 Assumptions for statistical test

The Kaplan-Meier analysis method assumes that censored individuals have the same prospect of survival as those who continue to be followed. Additionally, it is assumed that survival prospects are the same for early as for late recruits to the study.

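### The success bound in SAP 3.1.3.4 uses an untransformed Greenwood standard error; its one-sided error at 92.5% is about 6%, not the stated 5%, and a log(-log) or logit bound would bring it just under 5%

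*SAP*

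**What the plan says.** SAP 3.1.1 and 3.1.3.4 base the only hypothesis test on a confidence bound: "The null hypothesis will be rejected in favor of the alternative if the lower one-sided 95% confidence limit" is above 92.5%. SAP 3.1.3.4 then writes out the estimator, Greenwood's standard error and the bound. The bound is introduced by "The lower 95% confidence bound at t_i is calculated in SAS as follows" and is 100 × (S − probit(0.95) × SE), on the survival scale.

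SAP 3.1.2 sizes the registry by a different method: "An exact binomial calculation with the parameters in Table 3-1" (N = 1000, true rate 94.5%, boundary 92.5%), for a "meaningful change with 80% power and a one-sided α -level of 0.05". Attrition of 10% a year takes 1700 implanted patients to about 1000.

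SAP 3.1.3.2 restricts the analysis to implanted patients "still actively followed in the study at 45 days post implant will be included in the analysis". SAP 3.1.3.5 notes that the method "assumes that censored individuals have the same prospect of survival as those who continue to be followed". Protocol 4.1.1.2 and 4.2.1 ask for a Kaplan-Meier lower one-sided 95% bound but give no formula, so the choice is made only in the SAP. Neither document mentions a transformation or examines the error of the plain bound.

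**The concern.** At rates this close to 100%, the Greenwood standard error depends strongly on the estimate. When the truth is 92.5% and the estimate comes out high by chance, the standard error shrinks with it, the margin subtracted is too small, and the bound passes 92.5% more often than intended. The departure is in the direction of declaring success.

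The nominal 5% protects the registry's only confirmatory decision. The decision rule is also not the test used for sizing: at the planned N = 1000 the two reject from different counts.

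**Working it through.** **Inputs.** From SAP 3.1.1 and 3.1.2: null boundary 92.5%, assumed rate 94.5%, one-sided alpha 0.05, power 80%, N = 1000 with 5-year data, 10% annual attrition. The 1700 implanted is in SAP 3.1.2 and Protocol 4.1.1.3. The bound and standard error are in SAP 3.1.3.4. Not in the documents, and assumed: the timing of events, attrition rates other than 10%, and the exponential form of attrition.

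**1. The plan's own figure.** The exact binomial test of 92.5% with N = 1000 rejects from 939 complication-free patients. Its error is 4.93% and its power at 94.5% is 81.7%. Attrition: 1700 × 0.9^5 = 1004. The sizing reproduces.

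**2. The SAP bound without censoring.** Greenwood's formula then reduces to SE = √(S(1 − S)/N). For N = 1000 and probit(0.95) = 1.645:

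- 938 patients: SE = √(0.938 × 0.062/1000) = 0.007626; bound = 0.938 − 1.645 × 0.007626 = 0.92546. Passes.
- 937 patients: SE = 0.007683; bound = 0.92436. Fails.
- At the null value itself, SE = √(0.925 × 0.075/1000) = 0.008329. The standard error used at 938 is about 8% smaller (0.007626/0.008329 = 0.916), which is the source of the excess.

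The log(-log) bound is S^exp(1.645 × SE/(S × |ln S|)). At 938 it is 0.92415 and fails; at 939 it is 0.92525 and passes. The logit bound gives 0.92421 and 0.92530, the same decisions.

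Exact error at a true 92.5%, no censoring:

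| N | SAP formula rejects from (error) | log(-log), logit and exact binomial reject from (error) |
|---|---|---|
| 1000 | 938 (6.4%) | 939 (4.9%) |
| 1004 | 942 (5.9%) | 943 (4.6%) |
| 1700 | 1590 (5.6%) | 1591 (4.6%) |

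Part of the 6.4% is discreteness, but not all of the excess. Averaged over every N from 900 to 1100 the SAP formula gives about 6.2%, and from 1600 to 1700 about 6.0%. Log(-log) averages 4.6% and 4.7% over the same ranges.

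**3. With censoring.** Simulation: 1700 implanted; exponential attrition from implant; only patients active at 45 days analysed (about 1678 at 10%); Weibull event times from day 45 to year 5 with shape 0.5 (early), 1 (constant) or 2 (late), scaled to the stated 5-year rate; censoring independent of events. Each cell has 40,000 runs, with a Monte Carlo standard error of about 0.12 points. Error at a true 92.5%, early/constant/late:

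| Annual attrition | SAP formula, % | log(-log), % |
|---|---|---|
| 5% | 5.95 / 6.00 / 6.27 | 4.62 / 4.72 / 4.86 |
| 10% (plan) | 6.02 / 6.31 / 6.25 | 4.58 / 4.91 / 4.74 |
| 15% | 6.22 / 6.21 / 6.33 | 4.73 / 4.69 / 4.69 |

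The logit bound gives 4.64 to 4.96% over all cells. A separate simulation at 10% attrition, with time counted from a single origin and shapes 0.7, 1.0 and 1.5, gave 6.1 to 6.3% for the SAP formula and 4.7 to 4.8% for log(-log). In that run a plain log transformation stayed at 6.2 to 6.4% and arcsine-root at 5.4 to 5.6%, so the choice of transformation matters.

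**4. Practical size.** At a true 92.5% the verdict differs in 1.3 to 1.6% of registries. At 10% attrition this happens only when the estimate is about 93.6 to 93.8%, where the bounds differ by about 0.1 percentage point. At a true 92.0% the SAP formula passes 1.2 to 1.8% of the time and log(-log) 0.9 to 1.2%.

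**5. Power at 94.5%** (20,000 runs per cell, early/constant/late):

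| Annual attrition | SAP formula, % | log(-log), % |
|---|---|---|
| 10% | 93.0 / 91.0 / 89.3 | 90.9 / 88.6 / 86.2 |
| 15% | 90.6 / 87.1 / 83.4 | 88.0 / 83.7 / 79.0 |

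Power exceeds 80% at the planned attrition because the Kaplan-Meier analysis also uses the follow-up of patients who leave before five years, whereas the binomial sizing counts only the 1000 who complete.

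**The case against.** The arithmetic is not in dispute; the case against is about weight.

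- **Size.** The bound is a pre-specified large-sample interval, and its excess is a little over one point. At 94.5% and 10% attrition, the change turns 2 to 3% of registries from pass to fail, against about 1.5% at 92.5%. This can be read as an ordinary trade of error for power. It stands as a reason to call the effect modest. It does not make a 6% test a 5% test.
- **The alternatives are not exact.** Without censoring, over the 801 values of N from 900 to 1700, both transformed bounds reject one patient earlier than the exact test in 140, and the logit alone does so in another 39. Their uncensored error reaches 5.2% (log(-log)) and 5.3% (logit). This is correct, so agreement with the exact test is claimed only for the N tabulated. On average the two bounds give 4.6 to 4.7%, against 6.1% for the SAP formula, which in 296 of the 801 rejects two patients earlier than the exact test.
- **Timing.** Kaplan-Meier results go to FDA every six months (SAP 5.1 and 5.2), and Protocol 10.2 allows sponsor staff to be unblinded, so the success rule would change while the endpoint is visible. The change makes success harder, and SAP 5.5 provides for changes documented before the 5-year analysis. The timing should be stated openly but is no real obstacle.
- **Power sentence.** Holding the error near 5% does not require a new power statement in SAP 3.1.2. That is right; the sentence is optional.

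**Conclusion.** The concern holds. As written, the only confirmatory test has a one-sided error of 6.0 to 6.3% at a true 92.5% in every scenario simulated, against the stated 5%. Log(-log) and logit bounds give 4.6 to 5.0%. The simulated figures rest on assumed event timing and on censoring independent of events; the uncensored calculation needs neither and shows the same excess.

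The consequence is confined to a borderline result, but there a pass could be attributed to the choice of bound. The sample size and the 80% power statement are correct for the exact binomial test; for the Kaplan-Meier test at 10% attrition, 80% is conservative. The change should be made, though the registry does not depend on it.

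**What to change.** In SAP 3.1.3.4, replace the last formula with the log(-log) lower bound, 100 × S^exp(probit(0.95) × SE/(S × |ln S|)), where SE is the Greenwood standard error already defined there, or with the logit equivalent. Name the transformation explicitly, since the log and arcsine-root versions do not bring the error to 5%. Record the change, its date and its reason in a SAP approved before the 5-year analysis, as SAP 5.5 provides.

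Leave the sample size and the exact-binomial power statement as they are. Optionally, add a sentence to SAP 3.1.2 giving the power of the Kaplan-Meier test with the new bound at 94.5%: with 1700 implanted and independent censoring, about 86 to 91% at 10% annual attrition and about 79 to 88% at 15%, from late-weighted to early-weighted events.

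The cost is one formula and no extra patients. Power falls by about 2 to 3 points at 10% attrition and by 2.6 to 4.4 points at 15%. Among these scenarios it drops below 80% (79.0%) only with 15% attrition and events concentrated late.
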